### 2.6.3 Handling of missing values/censoring/discontinuations

For the FAS, the analysis will follow a LOCF approach with the specification that monotone missing values will be replaced by the last post-baseline observation prior to the missing timepoint. Intermittent missing values will be replaced by the mean of the closest non-missing adjacent values.

### 2.6.4 Supportive analyses

For supportive and sensitivity analyses of the primary analysis where p-values are presented, the one-sided non-inferiority p-value for the shifted hypothesis ( $\mu_{DI} - \mu_{PRN} \leq -\Delta$ ) will also be provided in addition to the p-value for the (unshifted) null hypothesis.

The primary analysis will be repeated for the PPS (LOCF) using the same methodology as outlined in [Section 2.6.2](#). Since this is a non-inferiority trial, the corresponding results obtained for the PPS are regarded as of almost equal importance for the interpretation. Any major discrepancies in the results across analyses will be investigated as necessary.

The same model as the one used for the primary analysis will be repeated for the FAS on observed data (as observed) as well as PPS (as observed). The primary efficacy variable D0 will be calculated as follows:

$$D0 = [(sum of non-missing BCVA1, BCVA2, \dots BCVA12 values) / k] - BCVA0$$

where k (k = 1, \dots, 12) is the number of non-missing BCVA values between month 1 and month 12, inclusively, and BCVA0, BCVA1, \dots BCVA12 are as defined in [Section 2.6.1](#).

Furthermore, the mean visit-averaged change from baseline in BCVA from month 1 to EoT, will be compared between the two treatments based on the assumption of a “Missing at Random (MAR)” process, i.e. assuming that the statistical behavior of a patient who drops out post-withdrawal is the same as that for a patient remaining in the study and sharing the same covariates and the same measurement history. This analysis will be based on a mixed model repeated measurement (MMRM). The MMRM model will be fit to all the BCVA data collected from month 1 to month 12 inclusive. The MMRM analysis will include subject as a random effect, and the following as effects:

Categorical variables

- treatment
- center

- visit

Continuous variables

- baseline BCVA

Interactions

- treatment by visit interaction
- visit by baseline BCVA interaction

A term for visit will be included in the repeated statement and an unstructured correlation matrix will be used thus allowing adjustment for correlations between time points within patients. A Kenward-Roger approximation will be used for the denominator degrees of freedom.

If the model with the unstructured correlation matrix fails to converge then the following correlation structures should be fitted; variance components, compound symmetry, first order autoregressive and Toeplitz. The value of the Akaike Information Criteria (AIC) should be considered to choose the most appropriate model. Note that, other things being equal, the model with the smallest AIC is preferred. In case of inadequate results, further modification of the model may be required.

Additional sensitivity analyses of the primary analysis (using the same methodology as outlined in [Section 2.6](#)) for FAS (LOCF) will be performed:

- using all data from baseline to EoS (visit-averaged change from baseline in BCVA from month 1 to EoS).  
This analysis is meant to additionally include the data collected between EoT and EoS for those patients who prematurely discontinue from treatment but stay in the study.
- excluding patients who discontinue treatment early but stay in the study
- using all data for patients who reach month 12 (i.e. completers, patients who do not prematurely discontinue treatment or the study early)

The LS (“adjusted”) means for each treatment arm and estimates of the difference (DI - PRN) will be given along with the respective two-sided, 95% CI. P-values will be presented for the treatment difference.

The difference in treatment effects will be illustrated graphically using a forest plot for each analyzed population for the primary analysis and each sensitivity and supportive analysis: the estimates of differences in visit-averaged change from baseline in BCVA from month 1 to the timepoint of interest, between the two treatment arms will be presented along with respective two-sided 95% CIs.

Furthermore, a frequency table presenting the number and percentage of patients based on FAS (LOCF) with a change of 5, 10, or 15 letters in BCVA from baseline at Month 12 will be provided.

KM curves and descriptive statistics will be provided for time to:

- first gain in BCVA from baseline of  $\geq 10$  letters
- first gain BCVA from baseline of  $\geq 15$  letters

for the FAS. The main focus of this study is to understand the effect of the two treatments of interest. Therefore, time to first gain  $\geq x$  letters (where  $x=10$  or  $15$  letters) will be derived for:

1. up to EoT

This means:

- if a patient prematurely discontinues treatment (EoT) but stays in the study longer (EoS > EoT), then only data up to EoT will be used for calculation and censoring
- if a patient prematurely discontinues treatment and the study at the same time, then data up to EoS will be used for calculation and censoring
- if a patient does not discontinue treatment early, then data up to EoS will be used for calculation and censoring

2. up to EoS

In case of no gain of post-baseline BCVA  $\geq x$  letters (where  $x=10$  or  $15$  letters), the duration will be censored at EoS.

The number and percentage of FAS patients with the aforementioned gain categorizations after their first three ranibizumab injections (i.e. change of  $5$ ,  $10$ , or  $15$  letters in BCVA from after their first three ranibizumab injections at Month 12) will also be presented.

Descriptive statistics will be produced for the baseline values, absolute values, and the change from baseline values to month 12 by overall stability compliance assessment (refer to [Section 2.1.1](#) for definition). In addition, descriptive statistics will be provided for the visit-averaged change from baseline in BCVA from month 1 to EoT (primary outcome) by overall stability compliance assessment for the total (not by treatment arm).

Additionally, gender subgroup analysis will be done for the primary analysis (based on FAS [LOCF]). Descriptive statistics will be provided for the visit-averaged change from baseline in BCVA from month 1 to EoT (primary outcome) for patients with the following characteristics (see [Section 2.1.1](#) for definitions of these characteristics):

- [REDACTED]
- the need of additional PRP treatment
- experiencing an incident leading to vitrectomy

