5.5.3.3 Instructions for use of investigational treatment

5.5.3.3.1 Treatment of study eye

Arm 1 (DI): after initial monthly treatment until maximum BCVA and no signs or no further change of disease activity, investigator will treat patients at own discretion. There will be no strict recommendations for retreatment or scheduling of upcoming visits except:

- patients need to be monitored at least every 3 months
- patients have to be retreated if any signs of disease activity occur.
- If relevant* loss of visual acuity is the reason for retreatment, next monitoring visit should be scheduled in 4 weeks.

*Relevant loss is defined as loss of visual acuity with a range outside the daily fluctuation of VA in DME patients. E.g. if 3-4 letters loss since last visit is accompanied by fluid in OCT it is highly likely that no daily fluctuation is present, but a true loss of BCVA. Investigator will decide whether VA-loss is relevant or a daily fluctuation and will document the decision and the reasoning in the source data

Due to flexibility of DI-arm, also treatment schemes like PRN, Treat & Extend or fixed dosing are allowed.

Arm 2 (PRN): investigator will treat patients in a PRN scheme, i.e. after initial monthly therapy until maximum BCVA and no signs or no further improvement of disease activity, patients will be monitored every month and retreated if any signs of disease activity occur.

For both treatment arms the following procedures apply:

Initial monthly therapy for both treatment arms: Beginning at baseline, injections are administered monthly until maximum visual acuity is achieved and no signs or no further improvement of disease activity are present.

Disease activity: both functional and morphologic parameters will be taken into consideration when defining disease activity. That could for example be:

- BCVA: change of BCVA
- OCT: increase of retinal thickness
- /FP/ophthalmoscopy: new signs of DME

If retreatment due to new disease activity is necessary, treatment should be continued until:

- maximum BCVA is achieved again or there is no improvement of BCVA compared to previous visit
- there is no further decrease of retinal thickness compared with previous visit
- there is no further regression and no further perspective of regression of other DME characteristics

The interval between 2 ranibizumab injections should not be shorter than 28 days.

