9.5 Analysis of secondary and other variables

9.5.1 Efficacy variables

The analysis of the secondary efficacy objectives will focus on the study eye only and it will be based on the FAS.

At all the time points assessed, each efficacy variable will be presented graphically (where appropriate) and descriptive statistics provided based on absolute values and changes from baseline.

Of note is that for patients randomized to the DI, no monthly visit and consequently no monthly reporting schedule exists. Therefore efficacy data collected by visit will be described on a bi-weekly schedule for the DI arm. Furthermore and in order to allow for a visualization of data of both arms on a monthly basis, data collected in between two monthly visits (e.g. at Month 5.5) will be reported at the following monthly visit.

For continuous and ordered categorical variables, changes from baseline will be compared between treatment groups using ANCOVA models (with the baseline covariate)/ T-test. For treatment differences, 95% confidence intervals will be calculated for differences of means (based on ANCOVA models).

Secondary Efficacy variables

The variables related to the secondary objectives are described below:

1. Mean change from baseline in BCVA from baseline to month 12.
2. Number visits and injections, and treatment free intervals
3. Changes in central subfield retinal thickness (CSRT) and foveal center point thickness by SD-OCT.
4. Comparison of changes of 1,2 or more steps in DRS retinopathy scale between treatment arms compared to baseline
5. ANCOVA analysis of primary outcome with the additional covariates “relevant changes of HbA1c, blood pressure, lipid level”

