## 5.2 Efficacy variables and populations for analysis

Table 5-3 describes and summarizes the efficacy variables of the study eye, and the populations for the planned analyses.

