**Table 5-3 Efficacy variables of the study eye**

		Analysis		
Efficacy assessment	Variable	Method	Population	Time Period
Primary efficacy				
BCVA	Visit-averaged change from baseline in BCVA	ANCOVA 	FAS (LOCF)	Baseline – EoT
		ANCOVA 	PPS (LOCF)	Baseline – EoT
		ANCOVA 	FAS (as observed)	Baseline – EoT
		ANCOVA 	FAS (LOCF)	Baseline – EoS
		MMRM 	FAS (LOCF)	Baseline – EoT
Secondary efficacy				
BCVA	BCVA change from baseline to month 12	ANCOVA 	FAS (LOCF)	Baseline - EoT
	BCVA change from baseline to month 12	ANCOVA 	FAS (LOCF)	Baseline - EoT
CSRT	CSRT change from baseline to month 12	ANCOVA 	FAS (LOCF)	Baseline - EoT
FCP thickness	FCP thickness change from baseline to month 12	ANCOVA 	FAS (LOCF)	Baseline - EoT

 The model includes the respective baseline variable as a linear covariate and the following categorical variables: treatment, center

 The model includes the respective baseline variable, relevant changes of HbA1c, blood pressure (systolic, diastolic), and lipid levels (cholesterol, HDL-cholesterol, LDL-cholesterol, triglycerides) as linear covariates and the following categorical variables: treatment, center

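### SAP Table 5-3 puts the MMRM on LOCF-filled data without visit terms, whereas SAP 2.6.4 makes it the missing-at-random analysis on collected data; the sample code in 5.2.1 also departs from 2.6.4 (supportive analysis, minor impact)

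*SAP*

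**What the plan says.** Protocol 9.4.4 promises a comparison under a missing-at-random assumption. SAP 2.6.4 delivers it as an MMRM and fixes the data: "The MMRM model will be fit to all the BCVA data collected from month 1 to month 12 inclusive". The model there has treatment, centre and visit as categorical effects, baseline BCVA, treatment-by-visit and baseline-by-visit interactions, a random subject effect, an unstructured matrix and Kenward-Roger degrees of freedom.

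SAP 5.2 says that Table 5-3 "describes and summarizes the efficacy variables of the study eye, and the populations for the planned analyses". Its MMRM row reads FAS (LOCF), Baseline to EoT, and points to footnote 1: "The model includes the respective baseline variable as a linear covariate and the following categorical variables: treatment, center". The same table has a separate row whose label begins "FAS (as observed".

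On missing data, SAP 2.6.3 says: "For the FAS, the analysis will follow a LOCF approach with the specification that" monotone gaps take the last post-baseline value. It adds: "Intermittent missing values will be replaced by the mean of the closest non-missing adjacent values".

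On visits, Protocol 9.5.1 notes that "for patients randomized to the DI, no monthly visit and consequently no monthly reporting schedule exists". Protocol 5.5.3.3.1 requires only that in the DI arm "patients need to be monitored at least every 3 months".

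SAP 5.2.1 prints illustrative MMRM code. SAP section 4 records no change from the protocol's analyses.

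**The concern.** Table and text describe two different analyses. LOCF in the MMRM row cannot be read as loose shorthand for the FAS, because the table has its own label for observed data.

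An MMRM allows for missing data only if the missing values are left missing. Once they are filled, it treats them as measured and has nothing left to adjust for. The only planned missing-at-random analysis would then be close to a copy of the primary LOCF ANCOVA. The forest plot in SAP 2.6.4 would still show it as a separate line, and agreement between the two lines would look like robustness.

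Filling here is not limited to dropouts. The DI arm has no monthly schedule, while the endpoint in SAP 2.6.1 needs twelve monthly values. Filled months are therefore expected mainly in one arm.

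**Working it through.** **1. The three sources side by side**

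| Item | SAP 2.6.4 | Table 5-3 | Code in 5.2.1 |
|---|---|---|---|
| Data | collected BCVA | FAS (LOCF) | placeholder |
| Visit and its two interactions | yes | no | yes |
| Centre | categorical | categorical | in MODEL, not in CLASS |
| Covariance | unstructured; common or by arm not said | not given | TYPE placeholder; GROUP by treatment printed, then re-instated in fallback steps 1-4 |
| Subject | random effect | not given | REPEATED only |
| Fallback | four structures, AIC considered | not given | ordered list of eight steps |

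The visit terms are missing only from the table.

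**2. The plan's own figures**

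Inputs (SAP 3): SD 10, margin 4, true difference 0, one-sided 0.025, power 90%. Normal approximation: n = 2 x 10² x (1.960 + 1.282)² / 4² = 131.4, so 132 per arm. The t-test has power 0.899 at 132 and 0.901 at 133, so the stated 133 reproduces. Raising 133 to 150 implies a dropout allowance of 1 - 133/150 = 11%.

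**3. Why filled data make the MMRM a near-copy**

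With twelve values per patient and every covariate crossed with visit, the MMRM visit-average contrast equals the ANCOVA on the visit average, for any unstructured matrix. A numerical check without centre gave 1.0180485 from both. The footnote 1 model with compound symmetry also matched the LOCF ANCOVA, to 1e-13. Centre as a main effect breaks exact equality only slightly:

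- 135 patients, 30 centres, estimated unstructured matrix, residual SD of the visit average 10, correlation 0.3 to 0.8, 300 datasets per setting: correlation of the two estimates 0.98 to 0.99, mean difference -0.01 to 0.02 letters, SD of the difference 0.34 to 0.42.
- 136 patients, 8 centres, covariance taken as known, 300 datasets: never more than 0.14 letters apart.

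**4. How much is filled**

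The documents do not give the DI visit spacing. If extension starts after month 3 (assumed) and visits fall at months 1, 2, 3, 6, 9 and 12, then months 4, 5, 7, 8, 10 and 11 are filled. That is 6 of 12, against none for a PRN patient seen every month.

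**5. What shift LOCF could hide (true difference 0; dropout split between arms assumed)**

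| Dropout, DI v PRN | LOCF ANCOVA | MMRM on LOCF | MMRM on observed data |
|---|---|---|---|
| 25% v 5%, early; half of DI on 3-month visits | -0.39 to -0.40 | -0.40 | -0.03 |
| 37% v 9%, missing at random | -0.44 | -0.44 | -0.01 |

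With 10% in both arms, close to the implied 11%, the shift is -0.02 to -0.03 letters (Monte Carlo SE 0.02 to 0.03), which is nil. Under strongly unequal dropout it is about 0.4/4 = 10% of the margin.

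**6. The code**

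- *Contrast.* With treatment, visit and their interaction all in CLASS, a treatment contrast is estimable only if each arm's treatment coefficient equals the sum of its twelve interaction weights. Here 12 x 0.083 = 0.996, against 1. The largest deviation from the estimable space is 0.0003 with all 24 weights at 0.083, and zero to rounding with 1/12. The text shows only nine positive weights; the other three may have been lost in extraction and are not counted.
- *Centre.* Treatment by visit gives 24 parameters and baseline by visit 12, so 36. About 30 centres (Protocol 4) as a factor add 29, giving 65. A numeric centre code outside CLASS adds one slope, giving 37.
- *Non-inferiority p-value.* SAP 2.6.4 requires it, but the PDIFF instruction has no LSMEANS statement to attach to. The sentence about a slice option likewise matches nothing in the code.
- *Covariance.* An unstructured 12 x 12 matrix has 12 x 13/2 = 78 parameters, or 156 if separate by arm, for 135 patients. Which one is the starting model is unclear.

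**The case against.** The best case against the point is that almost nothing turns on it. The MMRM is supportive, the trial is declared purely exploratory, and at the implied dropout allowance there is no shift to detect. Unequal dropout of 25% v 5% has no basis in the documents. SAP 2.6.4 is the specific text and should prevail over a summary table with a shared footnote. The code is called illustrative, and the ANCOVA code does put centre in CLASS, so its absence here is evidently a slip. A non-estimable contrast should be flagged when run, not silently misreported. As-observed ANCOVAs on FAS and PPS are also planned and use no filled values. All of this stands, and it sets the size of the point. It does not remove the contradiction: Table 5-3 says that it gives the analysis populations, and the as-observed ANCOVAs are not missing-at-random analyses.

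Three stronger readings are tempting, and the documents do not support them:

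- *That the fallback leads to a variance-components model with independent visits and a badly understated standard error.* This needs the unstructured fit to fail, the list to be stopped at its first entry, AIC to be ignored, and no subject effect to be fitted. SAP 5.2.1 never says to stop at the first structure that converges. SAP 2.6.4 has the structures fitted and AIC considered, so the two texts can be read together.
- *That variance components or GROUP must be removed.* With AIC choosing, the first can remain a candidate. For the second, 2.6.4 does not say whether the matrix is common to both arms. Each is a choice to be stated.
- *That the primary result is compromised.* Filled DI months enter the primary LOCF ANCOVA too, but the table error and the code defects described here do not touch it.

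**Conclusion.** The point holds as an inconsistency that should be corrected. Table 5-3 contradicts SAP 2.6.4 on the data and on the model terms, and the sample code does not implement 2.6.4. If the table is followed, the only planned missing-at-random analysis tests nothing about missingness and appears as separate support for the primary result.

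The impact is minor: one supportive estimate and its line on the forest plot, in a trial whose results are to be read descriptively. The simulated shift that LOCF could hide is nil at equal dropout near the implied 11%, and about -0.4 letters under strongly unequal dropout. The split of dropout between arms, the within-patient correlation and the DI visit spacing are assumptions. The text contradiction, the missing CLASS entry, the 0.996 sum and the unmatched instructions rest on no assumption.

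**What to change.** **Table 5-3.** Set the MMRM row to FAS (as observed). Give it its own footnote with the 2.6.4 terms: treatment, centre, visit, baseline BCVA, treatment-by-visit and baseline-by-visit.

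**Time period.** State whether values after EoT enter the MMRM. SAP 2.6.4 defines the comparison up to EoT but fits the model to all data to month 12, and these differ for patients who stop treatment and stay in the study. SAP 2.6 makes EoT the default.

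**Code.** Add centre to CLASS. Use exact weights: treatment -12 12, then twelve -1 and twelve +1, with DIVISOR=12, coded as DI minus PRN. Take the one-sided non-inferiority p-value from t = (estimate + 4)/SE on the Kenward-Roger degrees of freedom. Delete the PDIFF and slice sentences.

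**Covariance.** State whether the starting unstructured matrix is common to both arms or separate by arm. State that the ordered list in 5.2.1 gives the candidates and that AIC chooses among them. Align the random-subject wording in 2.6.4 with the REPEATED-only code.

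The cost is one table row, one footnote and a few lines of code and text. No data or patients are affected.

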## 2.7 Analysis of the key secondary objective

There are no key secondary objectives in this study.

## 2.8 Analysis of secondary efficacy objectives

The analysis of the secondary efficacy objectives will focus on the study eye only and it will be based on the FAS (LOCF), unless otherwise specified. Only data from baseline to EoT will be used for secondary objective analyses, unless specified otherwise. This means:

- if a patient prematurely discontinues treatment (EoT) but stays in the study longer (EoS is after EoT), then only data up to EoT will be used
- if a patient prematurely discontinues treatment and the study at the same time, then data up to EoS will be used
- if a patient does not discontinue treatment early, then data up to EoS will be used.

## 2.8.1 Secondary endpoints

The following secondary efficacy endpoints will be evaluated:

- Change of BCVA in ETDRS letters from baseline to month 12
- Number of visits, injections and TFIs
- Change of CSRT ( $\mu\text{m}$ ) from baseline to month 12
- Change in FCP thickness ( $\mu\text{m}$ ) from baseline to month 12
- Change in 0, 1, 2 or more steps in DRS from baseline to month 12
- ANCOVA analysis of primary outcome with the additional covariates: relevant changes of HbA1c, blood pressure (systolic, diastolic), and lipid levels (cholesterol, HDL-cholesterol, LDL-cholesterol, triglycerides)

Changes in CSRT and FCP thickness will be evaluated by the CRC assessing OCT images. Changes in DRS will be evaluated by the CRC scoring CF Photography and FA images and will be defined in 5 severity levels:

1. Mild non-proliferative retinopathy (NPDR)
2. Moderate NPDR
3. Severe NPDR
4. Proliferative DR
5. Status post panretinal laser coagulation - not gradable

